7.2.2. Study Day

Two different types of study days will be calculated for this study:

- Study Day will be calculated based on the date of the first dose of open label (OL) study drug in the OTTP and will be used to show start and stop days of assessments and events during the study. Study Day 1 will be the day of the first dose of OL study drug in the OTTP.
- Period Day will be calculated based on the date of the start of the study period during which the assessments or events will be performed or occur to show start and stop days of assessments or events during the study period.

Study Days will be calculated as follows:

- Study Day= (date of assessment or event – date of first dose of OL study drug in the OTTP) if the date of assessment or event is before the date of first dose of OL study drug during the OTTP
- Study Day= (date of assessment or event – date of first dose of OL study drug in the OTTP) + 1 if the date of assessment or event is on or after the date of first dose of OL study drug during the OTTP

Period Days of each study period, after screening, will be calculated as follows:

Efficacy Data:

- OTTP Day= (date of assessment or event – Baseline Visit) + 1
- SDP Day= (date of assessment or event – End Titration Visit) + 1
- DBRW Day= (date of assessment or event – date of randomization) + 1
- OLE Day= (date of assessment or event –End of Double-blind Randomized Withdrawal Visit) + 1

Safety Data:

- OTTP Day= (date of assessment or event – start date of first dose of OL study drug in the OTTP) + 1
- SDP Day= (date of assessment or event – date of the first dose of OL study drug in the SDP) + 1
- DBRW Day= (date of assessment or event – date of the first dose of DB study drug in the DBRW) + 1
- OLE Day= (date of assessment or event – date of the first dose of OL study drug in the OLE) + 1

7.2.3. Visit Windows

All scheduled (with the exception of scheduled visits for subjects requiring additional titration exceeding 10 weeks in the OTTP, end SDP visit, and end DBRW visit), unscheduled, and early termination assessments will be summarized by derived analysis visit per the below table, regardless if the visit was performed on-site or remotely. Visit dates will be mapped based on the scheduled Period Day of each visit, with adjusted analysis-defined visit windows as specified in Table 3.

Table 3: Visit Windows for Assessments or Measurements

Study Period	Adjusted-Defined Windows Visit	Scheduled Period Day	Clinical Laboratory ^a , Urinalysis, Serum Pregnancy, Physical Exams, ECG ^b			WPAI:SHP FOSQ-10	C-SSRS	Weight, Vital Signs, Alcohol, Urine Drug Screen, Urine, Pregnancy test ^c
			ESS, IHSS, CGIc and PGIC	2-18	n/a			
OTTP (no extension)	Week 1	8	n/a	n/a	n/a	n/a	2-10	2-18
	Week 2 (call)	15	n/a	n/a	n/a	n/a	11-17	n/a
	Week 3 (call)	22	n/a	n/a	n/a	n/a	18-24	n/a
	Week 4	29	19-42	n/a	n/a	n/a	25-35	19-42
	Week 6 (call)	43	n/a	n/a	n/a	n/a	36-49	n/a
	Week 8	57	43-63	n/a	n/a	n/a	50-63	43-63
	End Titration	71	64-max	n/a	n/a	n/a	64-max	64-max
	Extension Titration 1	71	64-77	n/a	n/a	n/a	64-77	64-77
OTTP (Ext 1 only)	End Titration	85	78- max	n/a	n/a	n/a	78-max	78-max
	Extension Titration 1	71	64-77	n/a	n/a	n/a	64-77	64-77
OTTP (Ext 1 & Ext 2)	Extension Titration 2	85	78-91	n/a	n/a	n/a	78-91	78-91
	End Titration	99	92 - max	n/a	n/a	n/a	92-max	92-max
SDP	End of SDP	15	2- max	2-max	2-max	2-max	2-max	2-max
DBRW	Week 1 (call)	8	n/a	n/a	n/a	n/a	2-10	n/a
	End of DBRW	15	2-max	2-max ^b	2-max	2-max	11-max	2-max
OLE	OLE Week 2	15	2-28	n/a	n/a	n/a	2-28	2-28
	OLE Week 6	43	29-70	n/a	n/a	2-70	29-56	29-70
	OLE Week 10 (call)	71	n/a	n/a	n/a	n/a	57-84	n/a
	OLE Week 14	98	71-133	n/a	n/a	71-133	85-112	71-133
	OLE Week 18 (call)	127	n/a	n/a	n/a	n/a	113-140	n/a
	OLE Week 22 (call)	155	n/a	n/a	n/a	n/a	141-161	n/a
	End OLE	169	134-max	2-max	134-max	162-max	162-max	134-max

^a Clinical laboratory includes hematology and chemistry labs; ^bOnly ECG is assessed at the End of DBRW; ^cIf the subject requires an in clinic visit (per local regulations) for week 10, week 18, or week 22 then all assessments in this column will be mapped to the same windows as the C-SSRS during the OLE.

Note: CGIc: Clinician Global Impression of Change. C-SSRS: Columbia-Suicide Severity Rating Scale. ECG: Electrocardiogram. ESS: Epworth Sleepiness Scale. FOSQ: Functional Outcome of Sleep Questionnaire. IHS: Idiopathic Hypersomnia Severity Scale. n/a: Not Applicable. OLE: Open-Label Extension. OTTP: Optimized Treatment and Titration Period. PGIC: Patient Global Impression of Change. DBRW: Double-blind Randomized-Withdrawal Period. SDP: Stable-Dose Period; WPAI:SHP: Work Productivity and Activity Impairment Questionnaire: Specific Health Problem.

Note: Period Day 1 and first dose of study drug of a study period are excluded from the visit windows as the study drug will be taken only after all the assessments scheduled to be collected on these days will have been performed.

For subjects requiring additional titration exceeding 10 weeks in the OTTP, nominal visits will be used from OTTP Week 8 Visit until the End titration Visit. Additionally, nominal visits will be used for the End SDP visit and End DBRW visit.

If multiple assessments or measurements are recorded within a single visit window (including unscheduled, repeated, and retest assessments or measurements as well as early discontinuation data), the following rules will be applied to determine the result from which assessment or measurement will be used for the summaries for that analysis visit.

- If there are two or more results within the same visit window, then the non-missing one closest to the scheduled Period Day will be used in the analysis.
- If two observations are equidistant from the scheduled Period Day, then the non-missing observation with the earliest collection date will be used in the analysis.
- If two observations are collected on the same day and this day is the closest to the scheduled Period Day, then the non-missing observation with the earliest collection time will be included in the analysis.

If a visit window does not contain any observations, then the data will remain missing.

Listings will include scheduled, unscheduled, repeated, retest, and early termination data per nominal visits.

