6.16.2. Handling of Early Terminations

If a subject terminates early from the study, either at his or her request or at the Investigator's discretion, the Investigator will record the reason(s) for Early Termination on the relevant eCRF page and notify the Sponsor/designee immediately.

- For all subjects who prematurely discontinue during the Double-blind Randomized Withdrawal Period, an attempt should be made to perform all procedures associated with the End of Double-blind Randomized Withdrawal Visit.

Clinical Study Protocol: JZP080-301 Amendment 2

- For all subjects who prematurely discontinue during periods other than the Double-blind Randomized Withdrawal Period, an attempt should be made to perform procedures associated with the End of Open-label Extension Visit.

It is vital to obtain follow-up data on any subject who terminated because of an AE, abnormal laboratory test, or ECG finding. In any case, every effort must be made to undertake safety follow-up procedures.

All subjects who early terminate from the study within 2 weeks of receiving the last dose should be asked to return 2 weeks later for the Safety Follow-up Visit.

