10.3. Laboratory Assessments

The continuous clinical laboratory assessments (hematology, chemistry, and urinalysis) will be summarized at each visit using descriptive statistics. The change from Screening will be provided at the end of SDP and end of OLE.

Shift tables will summarize changes in clinical laboratory assessments at the end of SDP and end of OLE with respect to baseline. Lab values are categorized into L1, low, normal, high, or H1 based on the lab reference range. L1 and H1 values are predefined per the lab vendor alert ranges and correspond to the extreme abnormal lower and higher ranges, respectively.

Abnormal laboratory assessments deemed clinically significant by the investigator will be reported as an adverse event.

A listing of subjects with abnormal value(s) according to the following criteria will be summarized using SAF:

- Any laboratory value that falls into the pre-defined low or high panic ranges (L1 or H1) per the Q2 Laboratory Range Chart.
- Alanine aminotransferase (ALT) or aspartate aminotransferase (AST) $\geq 3 \times$ Upper Limit of Normal (ULN) and total bilirubin $> 2 \times$ ULN
- AST or ALT $\geq 5 \times$ ULN,
- Creatinine ≥ 176
- Subjects positive for alcohol, urine drug screen or pregnancy assessments

All laboratory results, including pregnancy test, drug screen, and alcohol screen, will also be presented in subject data listings.

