10.5.2. ECG Abnormal Criteria

Abnormal quantitative ECG measurements will be identified in accordance with the following predefined markedly abnormal criteria (FDA 2005)

Observed values for QT interval, QTcB interval and QTcF will be classified as follows at each time point:

- > 450 msec
- > 480 msec
- > 500 msec

Change from baseline for QT interval, QTcB interval and QTcF will be classified as follows:

- >30 msec increase from baseline
- >60 msec increase from baseline

A listing of subjects meeting markedly abnormal criteria as well as a listing of subjects with abnormal ECG overall assessment will also be provided based on the SAF.

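### SAP Table 3 has no analysis visit for the laboratory, ECG, FOSQ-10 and WPAI:SHP values of subjects who stop during titration, so several summary tables omit them

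*SAP*

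**What the plan says.** Collection. For subjects who leave outside the randomized withdrawal period (DBRW), Protocol 6.16.2 says that "an attempt should be made to perform procedures associated with the End of Open-label Extension Visit". Protocol 7.5.4 lists that visit's content: physical examination, chemistry, hematology, urinalysis, 12-lead ECG, FOSQ-10 and WPAI:SHP, among others. Protocol 6.6 and 6.11.2 schedule ECGs and laboratory samples only at screening, the end of the Stable Dose Period (SDP), and the end of the open-label extension (OLE) or early termination. For a subject who stops in titration, the early-termination visit is therefore the only scheduled post-baseline laboratory and ECG assessment.

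Mapping. SAP 7.2.3 sends early-termination data through Table 3: "unscheduled, and early termination assessments will be summarized by derived analysis visit per the below table". It adds: "If a visit window does not contain any observations, then the data will remain missing". Listings are kept by nominal visit.

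Tables. SAP 10.3: "Shift tables will summarize changes in clinical laboratory assessments at the end of SDP and end of OLE with respect to baseline". Change from screening is given at the same two points. SAP 10.5 summarizes ECG values and changes by visit. SAP 10.5.2: "Observed values for QT interval, QTcB interval and QTcF will be classified as follows at each time point". SAP 9.4.5 summarizes open-label FOSQ-10 and WPAI:SHP by time point.

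**The concern.** The SAP undertakes to summarize all early-termination assessments through a table that has no row for some of them. Early leavers from the SDP and the OLE are caught by windows that open on Period Day 2. Only titration, the long period in which dose is being adjusted, lacks the equivalent, which suggests an oversight.

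What is at stake is the denominator. Protocol 9.9.3 bases safety analyses on the Safety Analysis Set, and Protocol 9.9.3.2 promises counts of subjects exceeding QTcF thresholds without limiting them to particular visits. SAP 7.6 declares no departure from either. Under the mapping rule, the laboratory shift table and the observed-QTc table contain no one who left in titration, even when a post-baseline value was obtained.

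**Working it through.** **Step 1: Table 3, read by period.** The extracted table text is broken, so the titration rows were checked for any alignment that would give these columns a window. None does. The last titration row reads "End Titration 71 64-max n/a n/a n/a 64-max 64-max"; the SDP row reads "End of SDP 15 2- max 2-max 2-max 2-max 2-max 2-max". The windows available to an early-termination value are:

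| Period | Labs, urinalysis, physical exam | ECG | FOSQ-10, WPAI:SHP |
|---|---|---|---|
| OTTP, including extension rows | none | none | none |
| SDP | Day 2 to max | Day 2 to max | Day 2 to max |
| DBRW | no window use (footnote: ECG only) | Day 2 to max | Day 2 to max |
| OLE | Day 2 to max | Day 2 to max | continuous from Day 2 (2-70, 71-133, 134 to max) |

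**Step 2: can another rule place the value?**
- *The End OLE window.* OLE Period Day (SAP 7.2.2) counts from the End of DBRW Visit for efficacy data and from the first OLE dose for safety data. A titration leaver has neither.
- *Nominal visits.* These apply only to extended titration (Week 8 to End Titration), End SDP and End DBRW.
- *Nearest scheduled visit.* SAP 7.2.4 confines this to visits affected by COVID-19.

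No rule remains, and an empty window stays missing.

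**Step 3: which outputs lose these subjects?**
- *Omitted:* laboratory by-visit, change and shift tables; by-visit ECG tables; observed QT/QTc categories; open-label FOSQ-10 and WPAI:SHP summaries.
- *Ambiguous:* the QTc change categories (more than 30 and more than 60 msec), for which SAP 10.5.2 names no time point.
- *Not affected:* adverse events (no visit windows); vital signs, weight, C-SSRS, ESS, IHSS, CGIc and PGIc, which all have titration windows; and the DBRW comparisons.
- The SAP describes no physical-examination table apart from weight, so that gap has no visible effect on a table.

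**Step 4: how many subjects?** Inputs from SAP 5.4: 112 randomized, 20% loss before randomization, about 140 enrolled.
- The plan's figure reproduces: 112 / (1 - 0.20) = 140.
- Lost before randomization: 140 - 112 = 28, or 28/140 = 20%.
- The documents do not divide the 28 between titration, the SDP and failure of the randomization criteria. If a share *s* falls in titration (assumption), the number is 28 × *s*:

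| *s* | Subjects | Share of 140 |
|---|---|---|
| 25% | 7 | 5% |
| 50% | 14 | 10% |
| 75% | 21 | 15% |
| 100% | 28 | 20% |

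Each figure falls if early-termination visits are not done.

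**Step 5: effect on a percentage.** Let *f* be the leavers' share of subjects with a post-baseline value, and p_e and p_c the abnormality rates in leavers and in the others. The rate over everyone is p_c + *f*(p_e - p_c), and a table without the leavers shows p_c. The gap is *f*(p_e - p_c). With *f* from 0.05 to 0.20, each percentage point of difference between the groups moves the rate by 0.05 to 0.20 points. If the rates are equal, the gap is zero. The documents give neither rate.

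**The case against.** The strongest reply is that little is hidden. SAP 10.3 and Protocol 6.15.1 turn clinically significant laboratory changes into adverse events, and Protocol 6.15.1 does the same for ECG changes. SAP 10.2 tabulates treatment-emergent events over the whole study on the Safety Analysis Set, including those leading to withdrawal of study drug. Panic-range laboratory values, liver-enzyme and creatinine threshold values and markedly abnormal ECGs are listed by subject on the same set. By-visit tables ordinarily contain only subjects seen at that visit. All of this stands, and it limits the consequence. It does not supply a shift or QTc category table with the full treated denominator, and it does not reconcile SAP 7.2.3 with its own table.

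Three stronger readings are tempting, and the documents do not support them:
- *That safety incidence in general is conditioned on tolerating the drug.* Adverse events, vital signs, weight and C-SSRS are summarized during titration.
- *That the omitted subjects are those who stopped for intolerance.* This is plausible but undocumented. Protocol 3.1.2 also withdraws subjects who do not reach an efficacious regimen, and Protocol 6.16.1 gives other reasons, such as a positive drug screen or pregnancy test.
- *That all 28 are affected, or that abnormality rates would be understated by a stated factor.* The 28 includes SDP leavers, whose values do have windows, and can include subjects who fail the randomization criteria at a visit where laboratory tests and ECG are scheduled. Any specific understatement needs rates that the documents do not contain.

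On QTc, SAP 10.5 names an early termination visit among the ECG recordings, so a programmer might use that label. SAP 7.2.3 as written does not permit it for the observed-value categories; for the change categories the question is open.

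**Conclusion.** The mapping gap is real and internal to the SAP. Following the stated rule, titration leavers' post-baseline values are absent from the tables marked as omitted in Step 3, and the QTc change categories need clarifying. The values are not lost, because listings and the adverse-event route remain. No efficacy conclusion changes.

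The number affected is at most 28 of 140 under the planned 20% loss. It is 7 to 28 if 25% to 100% of that loss falls in titration, which is an assumption, and smaller where the early-termination visit was not performed. The direction and size of any effect on abnormality percentages cannot be determined from the documents. The point merits a correction because the data are already to be collected and the change is cheap.

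**What to change.** 1. In SAP Table 3, add an analysis visit named OTTP Early Termination (OTTP Day 2 to max, for subjects who do not enter the SDP) covering laboratory tests, urinalysis, physical examination, ECG, FOSQ-10 and WPAI:SHP.
2. In the laboratory shift tables (SAP 10.3) and QTc threshold tables (SAP 10.5.2), add a worst post-baseline row on the overall Safety Analysis Set, so that each treated subject with a post-baseline value counts once. For laboratory shifts, give worst low and worst high separately. State that values obtained on DBRW placebo are excluded or shown separately, as SAP 10.2 does for treatment-emergent events.
3. In SAP 10.5.2, say which time points feed the QTc change categories.

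The cost is SAP wording and modest programming, with no new data. The early-termination row will pool values taken after very different lengths of exposure, and the abnormality percentages may look slightly less favourable.

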7.2.4. Visit and Assessment Changes Due to COVID-19

If a subject was not able to attend the site for a scheduled visit due to COVID-19 restrictions, then sites were instructed to collect data for select safety assessments (labs, ECG, physical exam) when the subject is next able to safely return to an on-site visit, even if those assessments would not normally be done at that visit. These assessments would be mapped to the nearest scheduled visit.

Changes in scheduled visits and corresponding assessments due to COVID-19 restrictions will be captured as text fields in the eCRF. In the eCRF completion guidelines, sites were provided instructions for capturing visits and/or assessments that were missed (not performed), delayed, or performed remotely. The following visit and assessment changes will be included in submission datasets:

- All on-site visits that were converted to remote visits due to COVID-19 restrictions will be flagged. This information will be captured in the eCRF and protocol deviation log.
- Missed visits and assessments are flagged if the “not done” field is indicated and the comment field indicates “COVID-19”.

7.2.5. Missing and Partial Data

Missing or partially missing concomitant medications and AEs start and stop dates will be imputed as described in **Error! No bookmark name given..** However, imputed dates will NOT be presented in the listings as their sole purpose will be for the classification of the medications as past, concomitant or post (refer to section 8.5) and the classification of the AEs as prior,

treatment-emergent or post (refer to section 10.2).

Missing questionnaire data will be handled as described in the following sections:

- ESS:
 - Individual item scores: section 9.1
 - Total score: section 9.1.2
- Missing data will not be imputed for key secondary endpoints, secondary endpoints, and other secondary endpoints. The handling of missing individual items for IHSS is summarized section 9.2.2. For TST and VAS, daily averages are calculated among non-missing records. Only if all daily values are missing for the last week of the SDP or DBRW, then the subject will be excluded from the comparative efficacy analysis for these endpoints.
- Missing safety data will not be imputed except for AEs and concomitant medication start and stop dates as described above.

7.3. Hypotheses Testing

The null and alternative hypotheses for the primary endpoint are:

$$H_0: \mu_{JZP-258} = \mu_{Placebo}$$

$$H_1: \mu_{JZP-258} \neq \mu_{Placebo}$$

Specifically, the null hypothesis states that there is no difference between the mean change in ESS from the end of the SDP to the end of the DBRW between the JZP-258 and placebo treatment groups. The alternative hypothesis states that the mean change in ESS is not equal between JZP-258 and placebo treatment groups.

Subjects who are randomized to continue JZP-258 in the DBRW will be treated as a single group regardless of the dose and regimen of JZP-258 received. Thus, there will be no multiplicity adjustments with respect to multiple doses for hypotheses testing.

7.4. Level of Significance & Multiplicity Adjustment

A hierarchical testing strategy will be implemented to preserve the family-wise Type 1 error rate at the 0.05 significance level for 2-sided testing of the primary and key secondary endpoints. The primary endpoint analysis will serve as the gatekeeper for sequentially testing the key secondary endpoints in the order (PGIC and IHSS). If the primary null hypothesis is rejected, then PGIC will be tested and if both null hypotheses for ESS and PGIC are rejected then IHSS will be tested. All tests will be 2-sided.

All other secondary endpoints, subgroup, and sensitivity analyses will be tested without multiplicity adjustments and nominal p-values will be provided.

Available safety data will also be summarized at the time of the final efficacy analysis. No statistical inferences are planned to be performed on any safety data.

7.5. Subgroups and Subgroup Analyses

Subgroup analyses will be conducted on the primary and key secondary efficacy endpoints for the following:

- Baseline Medication Group, if data are too sparse for at least one of the groups, then groups will be pooled (refer to section 7.1).
- JZP-258 stable dose regimen (e.g. once nightly vs twice nightly)
- Gender
- Region (North America vs Europe)
- High enrolling sites, based on the number randomized (Site XXX, Site XXX, vs all other)
- Baseline median BMI (kg/m^2) (\leq median vs $>$ median)
- Idiopathic Hypersomnia diagnosis (Long sleep vs without long sleep)
- With regard to COVID-19 considerations, Type of Visit (On-site vs Remote): On-site is defined as having both end SDP and end DBRW visits performed on site; Remote is defined as having at least one remote visit for either end SDP or end DBRW visit.

Should there be less than 20 subjects in any subgroup, then only summary statistics would be presented. The exception to this is the subgroup analysis for on-site vs remote; this subgroup analysis will be performed irrespective of subject numbers.

The output for estimating the treatment difference within subgroup will not be provided (least square [LS] means, standard error [SE], LS Mean Difference (95% confidence interval [CI]) or median difference (95% CI) and p-value) if the data are too sparse.

It should be noted that the study was not designed to detect treatment differences with high statistical power within any subgroups.

